Official Title of the Study: ITHACA: Development and Validation of a Multivariate Predictive Model for Prognosis in Head and Neck Cancer Patients Undergoing Radiotherapy - Ambispective Study.

NCT Number: Not yet assigned

Date of the Document: 17/10/2024

Background and Rationale

The importance of targeted and personalized treatment in head and neck cancers is underscored by the variability of tumor locations in this region and the necessity of preserving critical functions such as chewing, swallowing, speaking, and breathing. A personalized treatment approach that integrates clinical, laboratory, and instrumental data into an advanced predictive model for assessing survival and toxicity represents a significant advancement in managing head and neck cancers.

Radiomics plays a crucial role in this approach by extracting detailed morphological and biological information from radiological images, allowing for a more in-depth understanding of tumor pathology. Similarly, dosimomics provides valuable data on radiation dose distribution, aiding in treatment optimization and predicting potential side effects. By integrating radiomics and dosimomics, this study aims to enhance treatment outcome predictions while improving the management of associated toxicities, particularly those that impact patients' quality of life.

The ITHACA model seeks to incorporate a comprehensive range of data, including clinical parameters such as tumor stage, risk factors, and previous treatment responses, alongside radiological and dosimetric data. This holistic approach enables more precise predictions and facilitates more effective treatments tailored to individual patients.

Objectives

The study aims to develop and validate a multivariate predictive model for predicting:

1. Cancer recurrence
2. Survival
3. Treatment-related toxicity in patients with head and neck cancer

Materials and Methods

Study Design

- Type: Multicenter ambispective observational study utilizing clinical, laboratory, and instrumental data.

Study Population

- Inclusion: Consecutive patients with a histologically confirmed diagnosis of head and neck cancer.

Study Duration

The study is expected to last 10 years, beginning after ethics committee approval, with:

- Retrospective recruitment period: 2013–2023
- Prospective recruitment period: 2024–2034

Eligibility Criteria

Inclusion Criteria

Participants must meet all of the following criteria:

- Confirmed Diagnosis: Histologically confirmed head and neck cancer.
- Age: ≥ 18 years (adult patients).
- Complete Data Availability: Clinical data must include treatment details, follow-up information, and outcomes.
- Medical History: A comprehensive record of comorbidities and relevant medical background.

Exclusion Criteria

- Incomplete Data: Patients lacking essential clinical data for analysis.

Endpoints

Primary Endpoint

- Cancer Recurrence: Probability of recurrence after completing radiotherapy.

Outcome Evaluation Methods

- Evaluation Timing: 3, 6, 12, 24, and 36 months post-treatment.
- Methods: PET-CT, MRI, and CT scans to detect signs of recurrence.
- Clinical Documentation: Review of medical records to confirm recurrence episodes.
- Event Reporting: Inclusion of events identified during follow-up or reported by clinicians.

Secondary Endpoints

1. Overall Survival: Duration from the start of radiotherapy until death.
2. Disease-Free Survival: Time from completion of radiotherapy to cancer recurrence or death.

3. Treatment Toxicity: Incidence, type, and severity of acute and late radiotherapy-related toxicities.

Secondary Outcome Evaluation Methods

1. Regular Follow-up: Clinical assessments and radiological investigations to track health status and toxicities.
2. Data Recording: Use of clinical databases to monitor survival, disease progression, and toxicities.

Variables and Procedures

Clinical Variables

- Tumor Stage: Classified using the TNM system.
- Treatment Details: Radiotherapy, chemotherapy, and/or surgery specifics.
- Demographics: Age, sex, ethnicity.
- General Health & Comorbidities: Charlson Comorbidity Index or similar assessment tools.
- Risk Factors: Tobacco use, alcohol consumption, HPV exposure.
- Oncological History: Previous cancer diagnoses and prior oncological treatments.

Radiological Variables

- Pre-Treatment Imaging: Tumor size, adjacent tissue involvement, presence of lymph node metastases.
- Treatment Response: Tumor and lymph node changes, metabolic response in PET-CT.
- Recurrence Indicators: New lesions or changes in existing lesions.
- Post-Treatment Effects: Anatomical and tissue alterations caused by radiotherapy or surgery.

Radiomics Analysis

Radiomics analysis involves extracting quantifiable characteristics from radiological images to identify patterns associated with recurrence, survival, and toxicity.

Timing of Measurements

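### Undefined record-completeness conditions at entry remove patients with incomplete comorbidity or history data, and later imputation cannot recover them

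*Protocol*

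**What the plan says.** Under Study Population, the protocol describes its sample as "Consecutive patients with a histologically confirmed diagnosis of head and neck cancer". Under Eligibility Criteria the rule is conjunctive: "Participants must meet all of the following criteria". Two of the criteria concern the state of the record:

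- "Medical History: A comprehensive record of comorbidities and relevant medical background"
- "Complete Data Availability: Clinical data must include treatment details, follow-up information, and outcomes"

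The single exclusion criterion is "Incomplete Data: Patients lacking essential clinical data for analysis". The protocol does not say what makes a record comprehensive or which data are essential.

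Under Clinical Variables, comorbidity is itself one of the variables to be collected: "General Health & Comorbidities: Charlson Comorbidity Index or similar assessment tools". The same list contains "Risk Factors: Tobacco use, alcohol consumption, HPV exposure". Study Duration sets retrospective recruitment in 2013–2023 and prospective recruitment in 2024–2034. Timing of Measurements places collection of clinical, radiological and radiomics variables before treatment.

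**The concern.** A candidate predictor and the completeness of its record are being used as a gate to the cohort. When a comorbidity or history record falls short, the patient does not enter with a missing value. The patient does not enter at all. This is fixed by the eligibility text, so it cannot be left to a statistical analysis plan: such a plan can specify imputation only for patients who are in the data set.

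Three things are at stake for a study whose purpose is to develop and validate a prediction model, with the probability of recurrence as the primary endpoint.

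- **Events.** Every excluded patient who recurred is an event lost to model fitting.
- **Calibration.** If completeness of the record goes with prognosis that the model does not capture, or with the outcome, predicted risks may be wrong for patients with poorer records. Validation under the same criteria would use equally selected patients and could not show this.
- **Consistency.** With both terms undefined, centres may apply them differently. In retrospective charts the person judging completeness may already be able to see the outcome.

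**Working it through.** The protocol states no sample size, event rate or missing-data rate, so there is no figure of its own to reproduce. What follows has a textual step and two illustrations on assumed inputs.

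**Step 1: what the text makes a condition of entry.**

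| Baseline information | Status in the eligibility text |
|---|---|
| Comorbidities and medical background | Explicit inclusion criterion |
| Treatment details | Explicit, under Complete Data Availability |
| Tobacco, alcohol, HPV and other listed clinical variables | Only if read into the undefined *essential* |
| Imaging and dosimetric variables | Not expressly a condition |

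**Step 2: share of patients kept.** Assume k required items, each independently missing in a fraction m of charts. The share kept is (1 − m)^k. With an assumed 30% event rate, 1000 consecutive patients contain 300 events. If missingness is unrelated to outcome, 300 × (1 − m)^k of them remain.

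| m | Kept, k = 3 | Events left of 300 | Kept, k = 6 | Events left of 300 |
|---|---|---|---|---|
| 2% | 0.98^3 = 94.1% | 282 | 0.98^6 = 88.6% | 266 |
| 5% | 0.95^3 = 85.7% | 257 | 0.95^6 = 73.5% | 221 |
| 10% | 0.90^3 = 72.9% | 219 | 0.90^6 = 53.1% | 159 |

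Gaps tend to cluster in the same charts. In the extreme where all items are missing together, the share kept is 1 − m, that is 98%, 95% or 90%. The same figures apply if only one item is in effect required.

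**Step 3: effect on average predicted risk.** A simulation of 1,000,000 patients used a logistic outcome depending on one modelled predictor and one unmodelled prognostic factor (intercept −1, both coefficients 0.7), giving an event rate of 30.3%. About 30% of patients were excluded. The model was fitted to those kept, then applied to all.

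| Exclusion depends on | Kept | Events lost | Mean predicted | Observed | Observed/expected |
|---|---|---|---|---|---|
| Nothing (random) | 70.0% | 29.9% | 30.3% | 30.3% | 1.00 |
| The modelled predictor | 70.2% | 35.4% | 30.3% | 30.3% | 1.00 |
| The unmodelled factor | 70.2% | 35.4% | 27.9% | 30.3% | 1.09 |
| The outcome (40% of event patients, 25% of others) | 70.4% | 40.1% | 26.1% | 30.3% | 1.16 |

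Events are lost in every row. Average risk is miscalibrated only in the last two.

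**Step 4: direction.** The sign depends on who is excluded. With 40% of event patients and 25% of others excluded, the raw event rate among those kept is 0.303 × 0.60 / (0.303 × 0.60 + 0.697 × 0.75) = 0.182 / 0.705 = 25.8%. With the two exclusion rates exchanged it is 0.303 × 0.75 / (0.303 × 0.75 + 0.697 × 0.60) = 0.227 / 0.645 = 35.2%. Nothing in the protocol says which pattern applies, or whether either does.

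**The case against.** Several objections have force.

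- **Scope.** A reader might infer that every listed clinical variable is an entry condition, so that the protocol prescribes a complete-case analysis over the whole predictor set. Counting some 13 clinical items and 5% missing in each would give 0.95^13 = 51% kept. The text does not support this. Only comorbidity and medical background are named as a required baseline record. A count of 13 also takes in age and sex, which are seldom missing, and treatment items governed by a different criterion. A patient with a good history but no HPV status may well be eligible.
- **Consecutive sampling.** A reader might see a flat contradiction with the Study Population statement. Consecutive sampling is commonly understood as consecutive among eligible patients, so the tension is mild. What stands is that the resulting population is the well-documented subset, which that statement does not convey.
- **Bias.** A reader might conclude that the predicted recurrence probability will be biased. The history is due before treatment, so dependence on outcome would have to run through prognostic factors or later charting, and the protocol documents neither. Random exclusion, or exclusion depending only on a modelled predictor, left average calibration intact in the simulation.
- **Prospective part.** Baseline collection is planned there, so the problem lies mainly in the retrospective charts.
- **Screening records.** The protocol is silent on a log of excluded patients. That does not show that none will be kept.

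None of this alters the central fact that an incomplete comorbidity or history record is, as written, a ground for non-entry.

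**Conclusion.** The point holds in a bounded form, and the wording should be changed. As written, eligibility removes patients with an incomplete comorbidity or medical history record, and perhaps others, depending on how each centre reads *essential*. Analysis cannot undo that.

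Loss of events is certain wherever an excluded patient had one, but its size cannot be derived from the protocol. The range of 94% down to 53% kept rests on 3 to 6 required items, 2% to 10% missing in each, and independence. Clustering, or fewer required items, would keep more. Miscalibration for patients with poorer records is a risk conditional on completeness being tied to unmodelled prognosis or to outcome. The observed/expected ratios of 1.09 and 1.16 illustrate that condition and are not estimates for this study.

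The requirement that follow-up and outcomes be available is a separate issue, and this conclusion does not rest on it.

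**What to change.** 1. Delete the Medical History inclusion criterion. Comorbidity stays as a variable to be collected.
2. Limit the Incomplete Data exclusion to items without which a patient cannot be placed in the study: histology and radiotherapy dates.
3. State that missing baseline predictors are not a reason for exclusion, including under Complete Data Availability. Otherwise that criterion could still shut out the same patients.
4. Handle missing baseline predictors by multiple imputation with outcome, centre and year in the imputation model, and keep the complete-case fit as a sensitivity analysis. The detail can sit in the statistical analysis plan.
5. Report numbers screened and excluded by centre and period, so that any remaining selection can be judged.

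The cost is a change of eligibility wording, modest analysis work and a count of screened patients. No new patient procedures are needed. The downside is reliance on missingness at random given the imputation variables. The change is easiest to make before retrospective charts are screened out.

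### Does the Radiological Variables list let recurrence findings and post-treatment changes into the prediction model?

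*Protocol*

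**What the plan says.** Background and Rationale describes the model as seeking to draw on a wide range of data, "including clinical parameters such as tumor stage, risk factors, and previous treatment responses, alongside radiological and dosimetric data". It does not restrict these to baseline.

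Variables and Procedures, under Radiological Variables, has four items. One is pre-treatment imaging. The others are:
- for the response to treatment, "Treatment Response: Tumor and lymph node changes, metabolic response in PET-CT"
- for signs of relapse, "Recurrence Indicators: New lesions or changes in existing lesions"
- for changes seen afterwards, "Post-Treatment Effects: Anatomical and tissue alterations caused by radiotherapy or surgery"

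None is marked as a predictor or an outcome record.

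Timing of Measurements has three lines. Clinical, radiological and radiomics variables are collected before treatment. Tumour response and toxicity are monitored during it. Evaluations follow at 3, 6, 12, 24 and 36 months.

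The primary endpoint is recurrence after radiotherapy is complete, detected as follows: "Methods: PET-CT, MRI, and CT scans to detect signs of recurrence". The first secondary endpoint is "Overall Survival: Duration from the start of radiotherapy until death". The second counts from a later origin: "Disease-Free Survival: Time from completion of radiotherapy to cancer recurrence or death". The third concerns side effects: "Treatment Toxicity: Incidence, type, and severity of acute and late radiotherapy-related toxicities".

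The protocol gives no prediction time, performance target or sample size.

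**The concern.** A prediction model may use only what is known when the prediction is made. Three of the four radiological items become known, wholly or in part, after radiotherapy has begun. Read as a list of model inputs, the section raises three problems.

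1. **Recurrence.** New or changed lesions on imaging are what the primary endpoint looks for. A model given them would read the outcome instead of forecasting it.
2. **Late toxicity.** Tissue changes caused by radiotherapy overlap with the late-toxicity endpoint.
3. **Overall survival.** The clock starts with radiotherapy. Response, or any follow-up finding, can be recorded only in patients who live to the assessment, so it looks protective even with no effect (immortal-time bias).

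Validation would not expose any of this, because validation data holding the same variables would repeat the inflation. The baseline timing line also seems to put radiological variables as a whole before treatment, which cannot be true of all four items.

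**Working it through.** The protocol states no figure to reproduce. The check has two parts: what the text assigns, and how large the harm would be if the items were misused.

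**1. The list against the timing section**

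| Radiological item | Stage it fits | Natural role |
|---|---|---|
| Pre-treatment imaging | Baseline | Candidate predictor |
| Treatment response | During treatment, or early follow-up | Course of disease; a predictor only from a later landmark |
| Recurrence indicators | Follow-up | Record of the primary endpoint |
| Post-treatment effects | Follow-up (surgical changes may predate radiotherapy) | Mainly toxicity record |

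Every item has a stage. The baseline line conflicts with the list only if it is read as covering all four items and the next two lines are ignored.

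**2. Is any post-treatment item named as an input?**

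- Background and Rationale expresses an aim and names broad data types. It is not a predictor specification.
- The treatment responses mentioned there are called previous ones. They may be responses to earlier lines of treatment, which would match the Oncological History item under Clinical Variables.
- Dosimetrics Variables speaks of dose delivered, then of help with planning. It does not say that dose cut short by death or early stopping becomes a feature.
- Different time origins for overall and disease-free survival do not contradict each other.

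So no passage enters a post-treatment item as a predictor.

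**3. Size if misused (every input assumed)**

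*Leakage.* Take a normal baseline score x with separation d = √2 × z(AUC). For AUC 0.70, d = 1.414 × 0.524 = 0.742. Add a binary follow-up indicator by likelihood ratio: d·x + ln[se/(1 − sp)] if positive, d·x + ln[(1 − se)/sp] if negative. At se 0.80 and sp 0.90 the added terms are ln 8 = 2.08 and ln(0.20/0.90) = −1.50. Simulated with n = 200,000 and recurrence of 20%, 35% and 50%:

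| se / sp | Baseline AUC 0.60 becomes | Baseline AUC 0.70 becomes |
|---|---|---|
| 0.70 / 0.85 | 0.81 | 0.85 |
| 0.80 / 0.90 | 0.88 | 0.90 |
| 0.95 / 0.95 | 0.96 | 0.97 |

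The recurrence rate hardly matters.

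*Immortal time.* Assume exponential survival with rate −ln(S)/36, where S is 36-month survival. With S = 0.60, a 1.6-month course and response read 3 months later, the share dead before the reading is 1 − 0.60^(4.6/36) = 6.3%. If those deaths count as non-response and 60% of the rest respond, a response with no true effect shows a hazard ratio of 0.70. A landmark at the reading returns 1.005.

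A second set-up uses a null finding with a 10 to 30% chance of being recorded at each visit, S from 0.50 to 0.80, a 1.5-month course and censoring at 60 months. The hazard ratio is 0.37 to 0.63 when the finding is coded as fixed from the start of radiotherapy, and 0.98 to 1.04 with a landmark at the 3-month visit.

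The direction is certain under such misuse. The size depends on the assumptions, as the gap between 0.70 and 0.37 to 0.63 shows.

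**The case for a change.** The strongest case for a change is that prediction is the purpose of this study, so the moment of prediction is part of the study question and not a detail. Outcome ascertainment already has its own place under Endpoints. The radiological list stands instead beside plain candidate predictors such as stage, comorbidity and risk factors, with nothing to separate the roles. A sentence of clarification would cost nothing, and recruitment is planned to 2034.

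Part of this stands. The list mixes roles without labels, no prediction time is given for any endpoint, and the bias would be serious if all items were used as inputs from the start.

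The step from an unlabelled list to a defect does not stand. The heading covers variables and procedures, not predictors. A study that detects recurrence by imaging and follows toxicity with radiological investigations has to record these findings somewhere, and the item names largely declare their roles. Candidate predictors, prediction times and landmarks are usual content of a statistical analysis plan, and the absence of that plan from the material at hand is not a fault in the protocol.

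Nor is the delivered-dose variant a separate problem. It needs dose truncated by death to be used as a feature for survival counted from the start of radiotherapy, which nothing in the text plans. For endpoints counted from completion, delivered dose is already known.

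**Conclusion.** No change to the protocol is called for. The observation is accurate as far as it goes: four radiological items of mixed timing stand under one heading, unlabelled, and no prediction time is given. The harm depends on a use of the list that the document does not state and that its timing section does not suggest. The AUCs of 0.81 to 0.97 and the null hazard ratios of 0.37 to 0.63 rest wholly on assumed inputs and describe that hypothetical use.

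An analyst would ordinarily treat recurrence findings and radiotherapy-caused changes as outcomes, limit predictors to what is known at each endpoint's time origin, and use response only from a landmark. That landmark would require patients to be alive for overall survival, and alive and recurrence-free for recurrence and disease-free survival.

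The conclusion rests on reading the list as a record of what is collected. It would change if an analysis plan entered recurrence indicators or follow-up changes as predictors, or entered response without a landmark.
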